11.4.6 Laboratory Safety Assessments

The laboratory safety analyses (hematology, biochemistry, urinalysis, viral serology and drugs of abuse, and alcohol test) will be performed by the local laboratory at site. The following laboratory safety parameters will be measured (Table 12):

Table 12. Laboratory Safety Parameters

Category	Laboratory Parameter	Units		
		Conventional	SI	Site Laboratory
Biochemistry	Alkaline phosphatase Alanine aminotransferase (SGPT) Aspartate aminotransferase (SGOT) Calcium Chloride Creatinine Gamma glutamyl transferase (GGT) Glucose Lactate dehydrogenase (LDH) Potassium Sodium Bilirubin; Total Bilirubin Triglycerides	U/L U/L U/L mg/dL mEq/L mg/dL U/L mg/dL U/L mEq/L mEq/L mEq/L mg/dL mg/dL mg/dL	µkat/L µkat/L µkat/L mmol/L mmol/L µkat/L mmol/L µkat/L mmol/L µkat/L mmol/L mmol/L mmol/L	IU/L IU/L IU/L mg/dL mmol/L mg/dL IU/L mg/dL IU/L meq/L mmol/L mg/dL mg/dL mg/dL mg/dL

Date: 13 December 2023

Sponsor: Atlas Molecular Pharma S.L. Study Code: ATL001-PI-CEP NCT No.: 05647343

Category	Laboratory Parameter	Units		
		Conventional	SI	Site Laboratory
	Urea	mIU/L	mIU/L	uIU/mL
	Thyroid stimulating hormone (TSH)			
	Thyrotropin	mIU/L	IU/L	mIU/mL
	Follicle stimulating hormone (<2 years post-menopausal females	mL/min	mL/min	mL/min
	only) (FSH)			
	eGFR (only at Screening)			
Hematology	C reactive protein (CRP)	mg/L	nmol/L	mg/L
	Ferritin	ng/mL	pmol/L	ng/mL
	Hemoglobin	g/dL	g/L	g/dL
	Erythrocytes; Red Blood Cells	×10 ⁶ /µL	×10 ¹² /L	×10 ⁶ /µL
	Leukocytes; White Blood Cells	/µL	×10 ⁹ /L	×10³/µL
	Basophils	/µL	×10 ⁹ /L	×10³/µL
	Eosinophils	/µL	×10 ⁹ /L	×10³/µL
	Lymphocytes	/µL	×10 ⁹ /L	×10³/µL
	Monocytes	/µL	×10 ⁹ /L	×10³/µL
	Neutrophils	/µL	×10 ⁹ /L	×10³/µL
Urinalysis	Color	-	-	-
-	Specimen Appearance	-	-	-
	pH	-	-	-
	specific gravity	g/mL	kg/m3	Ratio
	Bilirubin; total bilirubin	Neg./Pos.	Neg./Pos.	Neg./Pos.
	Glucose	Neg./Pos.	Neg./Pos.	Neg./Pos.
	Ketones	Neg./Pos.	Neg./Pos.	Neg./Pos.
	Nitrite	Neg./Pos.	Neg./Pos.	Neg./Pos.
	Occult blood	-	-	Neg./Pos.
	Erythrocytes; Red Blood Cells	RBC/µL	-	/HPF
	Leukocytes; White Blood Cells	WBC/µL	-	/HPF
	Albumin	mg/L	g/L	mg/dL
	Total Protein	mg/L	g/L	mg/dL
	Uric acid crystals	Neg./Pos.	Neg./Pos.	Neg./Pos.
Drugs of abuse and alcohol parameters*	Amphetamine	-	-	-
	Barbiturates	-	-	-
	Benzodiazepine	-	-	-
	Ethanol	-	-	-
	Cocaine	-	-	-
	Opiate	-	-	-
	Phencyclidine	-	-	-
	Cannabinoids	-	-	-
	Cotinine	-	-	-
Viral Serology*	Hepatitis B Virus Surface Antigen (HBsAg)	-	-	-
	Hepatitis C Virus (HCV) Antibody	-	-	_
		-	-	-

Date: 13 December 2023

Sponsor: Atlas Molecular Pharma S.L.

Study Code: ATL001-PI-CEP

NCT No.: 05647343

Category	Laboratory Parameter	Units		
		Conventional	SI	Site Laboratory
	Human Immunodeficiency Virus (HIV) antibody I and II COVID-19			

^{*}Only at Screening and/or Baseline (Day 1).

The observed values will be recorded in the eCRF and assessed as "normal" or "abnormal". Abnormal findings will be assessed as "clinically significant" or "not clinically significant".

Blood and urine samples will be collected at specific time points throughout the study. The timing of the assessments is described in Section 8.2.1 and and Table 1.

Details on collection, storage and handling of blood and urine samples will be provided in the respective Laboratory Manual.

Blood and Urine Volumes

The maximum amount of blood and urine to be collected for laboratory safety assessments (hematology, biochemistry, and urinalysis) along the study are 50 mL and 50 mL, respectively. For each day when a laboratory safety assessment sampling is collected, 5 mL of blood and 5 mL of urine will be withdrawn.

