2.1 Schedule of Activities (SoA)

Table 1. Schedule of Activities

	Screening period						Tr	eatment p	eriod					Follow-u	Follow-up period	
								Hospital discharge [†]	FU-V1	FU-V2						
Day	Day -30 to Day -1	Baseline (Day 1)										Day 2 and Day 6	3 days after the last IMP dose	30 days after the last IMP dose		
Assessment time				5 min 30 min 1 h 1:30 h 2 h 2:30 h 3 h 4 h 6 h 8 h 12 h 5 min) (±50 min) (±10 min) (±10 min) (±10 min) (±15 min) (±15 min) (±30 min) (±30 min) (±30 min) (±30 min)						24 h (±30 min)						
Informed consent	Х															
Inclusion/Exclusion criteria	х	X ¹														
Randomization		×			•											
Demographic data	Х															
Medical history	Х	X ²												X ²	X ²	
Physical examination	Х	Х	,		'		Х						Х	Х	Х	
Vital signs³	Х	Х	,				Х						Х	Х	Х	
Laboratory safety assessments ⁴	х	Х					х						х	х	х	
Viral serology⁵	Х															
Drug of abuse and alcohol screen	х	Х														
Pregnancy test (females only) ⁶	Х	X ⁷	·													

CONFIDENTIAL

Page 10 of 60

Date: 13 December 2023

Sponsor: Atlas Molecular Pharma S.L. Study Code: ATL001-PI-CEP NCT No.: 05647343

	Screening period		Treatment period										Follow-up period			
	Screening visit		Hospital Admission Hospital discharge†								FU-V1	FU-V2				
Day	Day -30 to Day -1	Baseline (Day 1)								3 days after the last IMP dose	30 days after the last IMP dose					
Assessment time		Pre-dose (0 h)				1:30 h (±10 min)	2 h (±10 min)	2:30 h (±15 min)	3 h (±15 min)	4 h (±30 min)	6 h (±30 min)	8 h (±30 min)	12 h (±30 min)	24 h (±30 min)		
ECG	х	Х					Х							Х	х	Х
PK blood sampling		X ⁷	Х	Х	Х	Х	Х	Х	Х	Х	Х	Х	Х	Х		
Concomitant medications	х	х	х	х	х	х	х	х	х	х	х	Х	х	х	х	х
Adverse events ⁸	X 9	X9	Х	Х	Х	Х	х	х	х	х	Х	Х	Х	Х	х	х

ECG, electrocardiogram; FU-V, Follow-up Visit; h, hour; IMP, investigational medicinal product; min, minutes; PK, pharmacokinetics

- [†] Subjects will be discharged at Day 2 and Day 6 after completing their assessments.
- ¹ Assessment of changes in inclusion/exclusion criteria
- ² Assessment of changes in the medical history
- ³ Vital signs include: blood pressure, pulse rate and body temperature
- ⁴ Laboratory safety assessments include: hematology, biochemistry, and urinalysis
- ⁵ Viral serology will comprise human immunodeficiency virus (HIV) I and II, hepatitis B virus surface antigen (HBsAg) and hepatitis C virus testing, and coronavirus disease (COVID)-19 testing by polymerase chain reaction (PCR)

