6.2.2 Summary of Clinical Findings

This is a first-in human study designed to assess the safety, tolerability, and PK of oral doses of ATL-001 in healthy adult volunteers, and thus, there is no available clinical research data to date on the IMP.

Nevertheless, other formulations of ciclopirox olamine have been previously orally administered to humans. A Phase I study assessed the tolerability and biologic activity of oral ciclopirox olamine in subjects with relapsed or refractory hematologic malignancy (NCT00990587). The drug was rapidly absorbed and cleared with a short half-life. Ciclopirox had a $t_{1/2}$ of less than 6 hours after both single and repeated administration. Despite the short apparent elimination $t_{1/2}$, the ciclopirox C_{max} values obtained following 80 mg/m² ciclopirox olamine once or four times daily exceeded 1 μ M. Plasma concentrations of an inactive ciclopirox glucuronide metabolite were greater than those of ciclopirox. Grade 3 gastrointestinal dose-limiting toxicities (DLTs) and bowel inflammation were observed in 3 out of the 4 subjects in the cohort receiving 80 mg/m² four times daily. No DLT was observed at 40 mg/m² once daily [7].

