7. STUDY OBJECTIVES AND ENDPOINTS

Objective	Endpoint
Primary	
The primary objective of the study is to investigate the safety and tolerability of ATL-001 in healthy subjects	Incidence of adverse events (AEs) and of clinically relevant changes in vital signs values, electrocardiogram (ECG) data, physical examination and laboratory safety data for five different doses of ATL-001
Secondary	
To determine the PK of ATL-001 in healthy subjects	Derived pharmacokinetic parameters for ATL-001 including area under the plasma drug concentration versus time curve (AUC _(0-last) , AUC ₍₀₋₁₂₎ , AUC ₍₀₋₂₄₎), maximum observed plasma drug concentration (C _{max}), time to maximum observed plasma drug concentration (t _{max}), apparent terminal half-life (t _{1/2}), apparent total body clearance (CL/F) and apparent volume of distribution (Vz/F), as appropriate

Version: 4.0

Date: 13 December 2023

Sponsor: Atlas Molecular Pharma S.L. Study Code: ATL001-PI-CEP

NCT No.: 05647343

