8.1.3 Dose-Limiting Toxicities

In case of any occurrence of one of the following criteria in one of the cohorts, no further dose escalation will be applied in subsequent cohorts:

- ≥ 1 subject of one cohort reporting grade ≥2 AEs up to FU-V1 (3 days after the last IMP dose)
- Corrected QT interval by Fredericia (QTcF) ≥500 ms and/or an increase of QTcF from baseline of ≥ 60 ms, confirmed by repeated ECGs, in at least 1 subject up to FU-V1 (3 days after the last IMP dose)

NOTE: Only toxicities with a clear-cut alternative explanation will be deemed non-DLT.

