5.4.3.4 Clinical Laboratory Test

To evaluate the safety profile the following laboratory tests will be performed:

- **Hematology**

- Hemoglobin
- Erythrocytes
- Leukocytes
- Neutrophils
- Lymphocytes
- Monocytes
- Eosinophils
- Basophils
- Ferritin
- C reactive protein (CRP)

- **Biochemistry**

- Alkaline phosphatase
- AST / SGOT
- ALT / SGPT
- Gamma-glutamyl transferase
- Creatinine
- Glucose
- Total Bilirubin
- Lactate dehydrogenase
- Triglycerides
- Calcium
- Chloride
- Potassium
- Sodium
- TSH
- BUN

- **Urinalysis**

- Quantitative
 - pH
 - Specific gravity
 - Microalbumin
 - Protein
- Qualitative
 - Urine bilirubin (Positive / Negative /Not Done)
 - Ketones (Positive / Negative /Not Done)
 - Nitrite (Positive / Negative /Not Done)
 - Occult blood (Positive / Negative /Not Done)
 - Acid Urate Crystals (Positive / Negative /Not Done)
 - Urine glucose (Positive / Negative /Not Done)
- Microscopic analysis quantitative (will be analyzed as qualitative)
 - RBC Casts (in range / above the range/ missing)
 - WBC Casts (in range / above the range/ missing)
- Microscopic analysis qualitative
 - Urine Appearance (Normal / Abnormal /Not Done)
 - Urine Color (Normal / Abnormal /Not Done)

For each parameter, summaries will be presented for the Screening, Baseline, and each scheduled post-baseline visit.

For each quantitative laboratory parameter, the values, and changes from baseline will be summarized by placebo / dose-level cohorts (including number of observations, missing, mean, SD, median, Q1, Q3, minimum, and maximum) will be calculated for each visit.

The decimal precision for each parameter will be based on the maximum number of decimals to which the results were reported on the eCRF.

If a result for a parameter that is normally considered quantitative is reported as a range (i.e., the result for basophils is reported as '<0.01'), this value will be not considered in the summary table. All the values reported will be included in the respective listing.

Lab Original results with ND/ NA/ NE/ UNK/ NQ/ UN etc: will not be evaluated or used for the analysis purpose.

All biochemistry, hematology, and urinalysis data will be listed.

The listings will be sorted by placebo /dose-level cohort, subject, parameter, visit and timepoint (if applicable).

The results and normal ranges will be displayed to the same decimal precision in the listings.

The clinically significant abnormal values will be flagged.

Notes:

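### Platelets are in neither the protocol's nor the SAP's haematology list, so no platelet data are planned although laboratory safety is part of the primary endpoint

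*Protocol*

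**What the plan says.** Protocol Section 11.4.6 introduces the laboratory panel with "The following laboratory safety parameters will be measured (Table 12". The haematology block of Table 12 holds ten rows: C reactive protein, ferritin, haemoglobin, red cells, white cells ("Leukocytes; White Blood Cells") and five white-cell types. Of these results the section says "The observed values will be recorded in the eCRF", with each value classed as normal or abnormal and abnormal values judged for clinical significance.

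SAP Section 5.4.3.4 opens with "To evaluate the safety profile the following laboratory tests will be performed" and names the same ten haematology items in a different order. Its notes name FSH and glomerular filtration rate as shown in a listing only; platelets are not mentioned there either.

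Haematology belongs to every safety draw. The footnote to the Schedule of Activities (Protocol Section 2.1) reads "Laboratory safety assessments include: hematology, biochemistry, and urinalysis".

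The primary endpoint (Protocol Section 7) is "Incidence of adverse events (AEs) and of clinically relevant changes in vital signs values, electrocardiogram (ECG) data, physical examination and laboratory safety data" across the five doses. One of the dose-limiting toxicity criteria (Section 8.1.3) is "≥ 1 subject of one cohort reporting grade ≥2 AEs up to FU-V1 (3 days after the last IMP dose". Section 12.1.1 counts an abnormal laboratory finding as a possible adverse event and grades events by NCI-CTCAE. Section 12.2 makes an asymptomatic laboratory finding reportable when it is clinically significant, meets the criteria for a serious event, or leads to discontinuation.

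**The concern.** The panel covers red cells, haemoglobin and white cells with a five-part differential, but not the third blood-cell line. No reason is given. The protocol describes the trial in these words: "This is a first-in human study designed to assess the safety, tolerability, and PK of oral doses of ATL-001 in healthy adult volunteers". Its primary question is safety, and its results are meant to guide the choice of doses for later studies (Section 6.3).

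Two things are at stake. First, an asymptomatic fall in platelets can enter the dose-limiting toxicity and stopping rules only if somebody has a count to look at, and the plan does not ask for one. Second, the final report could state that no haematological effect was seen without platelets having been measured. Without a pre-dose value there is also no baseline, so a change from baseline could not be computed later even if an isolated count came to light.

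**Working it through.** The point is mainly one of content, so the two lists are set side by side first. The plan states no figure to reproduce.

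**1. Haematology items**

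| Item | Protocol Table 12 | SAP 5.4.3.4 |
|---|---|---|
| Haemoglobin | yes | yes |
| Erythrocytes | yes | yes |
| Leukocytes | yes | yes |
| Neutrophils | yes | yes |
| Lymphocytes | yes | yes |
| Monocytes | yes | yes |
| Eosinophils | yes | yes |
| Basophils | yes | yes |
| Ferritin | yes | yes |
| C reactive protein | yes | yes |
| Platelets | no | no |

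Both lists have ten items and the sets are identical. An extraction fault is unlikely: each Table 12 haematology row is intact with its own units, nothing in the block is marked as redacted, and the separately ordered SAP list agrees item for item. Neither platelets nor thrombocytes are named elsewhere, including in the eligibility criteria, the schedule, the stopping and dose-limiting toxicity rules and the listings.

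**2. Scheduled draws per subject** (Protocol Sections 8.2.1.1 to 8.2.1.3)

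- Before dosing: Screening; Day 1 pre-dose = 2
- After dosing: Day 1 at 2 h; Day 2; Day 5 at 2 h; Day 6; FU-V1; FU-V2 = 6
- Total = 2 + 6 = 8

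Five of the six post-dose draws (all but FU-V2) fall inside the dose-limiting toxicity window, which ends at FU-V1.

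**3. What a prospective change would reach**

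Protocol Section 13.4 says that an analysis was done after Cohort 4 was completed and before Cohort 5 was enrolled. A change made from Version 4.0 onwards therefore reaches Cohort 5 only.

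- Cohort 5, all draws: 8 subjects × 8 = 64
- Cohort 5, post-dose on active drug: 6 subjects × 6 = 36

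For comparison, the whole trial:

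- All draws: 40 × 8 = 320
- Before dosing: 40 × 2 = 80
- Post-dose on active drug: 30 × 6 = 180

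**4. Room within the blood volume** (Protocol Section 11.4.6: 5 mL per sampling day, 50 mL maximum)

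- Day 1 pre-dose and Day 1 at 2 h share a day, so there are 7 sampling days: 7 × 5 = 35 mL
- Counted per draw instead: 8 × 5 = 40 mL

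Both totals are below 50 mL.

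**The case against.** The strongest reply is that nothing in the documents requires platelets. No objective, rule or planned analysis names them, and no passage contradicts another. Gastrointestinal toxicity is the only risk in Table 2, and the non-clinical and clinical summaries (Sections 6.2.1, 6.2.2 and 6.4) report no platelet signal. The first-in-human label applies to this formulation, since other oral formulations of ciclopirox olamine have already been given to people. All of this stands. It makes the point an improvement to the panel and not the correction of an error.

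Three stronger readings are tempting, and the documents do not support them.

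- *The trial cannot see a platelet effect.* The definition of an adverse event is not confined to Table 12. A clinically significant count that the local laboratory happened to report could be recorded and graded, and a bleeding event could surface through adverse event reporting or examination. What is missing is planned collection and summary.
- *The target disease makes platelets essential.* Section 6.1 mentions haematological abnormalities, but the one it describes is haemolytic anaemia. Haemoglobin and red cells cover that, and the participants are healthy volunteers.
- *A total of 320 platelet results is lost and can be restored.* That total includes screening and pre-dose draws, placebo subjects and cohorts already completed. Whether earlier counts exist is unknown.

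A further reply is that the DSMB may recommend adding safety assessments (Section 8.1.1). That is a route to the fix and does not fill the gap.

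**Conclusion.** The omission is real and is the same in both documents. As planned, one blood-cell line has no collected value, flag, change from baseline or summary, in a trial whose primary endpoint includes laboratory safety data and whose escalation and stopping rules can be met by abnormal laboratory findings. What the trial can conclude is affected: a statement of no haematological effect would not cover platelets. The consequence is bounded, because there is no known signal in the documents and the adverse event route remains open.

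The gain from acting now is up to 64 platelet results in Cohort 5, 36 of them post-dose on active drug. This assumes that Cohort 5 draws have not yet been taken; any already taken fall under the same retrieval rule as Cohorts 1 to 4.

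Two further assumptions come from outside the documents. The first is that the local laboratory's blood count already yields platelets, so that no extra tube is needed. The second is that the eCRF follows the two lists. Neither the Laboratory Manual nor the eCRF was available to check.

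**What to change.** 1. Add a row for platelets (×10³/µL; ×10⁹/L) to the haematology block of Protocol Table 12, a field to the eCRF haematology form, and the parameter to SAP Section 5.4.3.4 and its table shells. The existing provisions for flags, changes from baseline and summaries then apply without further text.
2. For Cohorts 1 to 4, search the existing site laboratory reports for every subject and every scheduled draw, whatever the treatment. Use values only where they exist, report how many were found, and do not describe the data as complete.
3. Where no values exist, state in the clinical study report that platelets were not assessed in those cohorts, and restrict any conclusion of no haematological effect to the parameters measured.
4. If platelets were left out on purpose, give the reason in one sentence in the protocol and keep the restriction in item 3 for all cohorts.

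The cost is one table row, one eCRF field, one SAP parameter with its shells, and the data entry. No visit is added, and no tube on the assumption above. The main drawback is that data for Cohorts 1 to 4 may be incomplete, and that those cohorts have already been analysed once, so any values added later should be identified as such.

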11.5 Appropriateness of Measurements

Standardized methods for measurements of safety and PK variables will be used.

Version: 4.0

Date: 13 December 2023

Sponsor: Atlas Molecular Pharma S.L. Study Code: ATL001-PI-CEP

NCT No.: 05647343

12. ADVERSE EVENTS

AEs will be daily recorded by the subject in the subject diary. All AEs will be reported and documented as stated below. The investigator will instruct study subjects on how to complete the subject diary.

The Investigator is responsible for appropriate medical care of the subjects during the study.

The Investigator remains responsible for following through an appropriate healthcare option with study subjects who experienced AEs that are serious or that caused the subject to discontinue before completing the study.

12.1 Definitions

12,1,1 Adverse Event

Adverse events and grading criteria will be defined based on Common Terminology for Adverse Events (NCI – CTCAE), following the most updated version from National Cancer Institute (v. 5.0 or higher when available).

Any untoward medical occurrence in a clinical trial subject administered a medicinal product and which does not necessarily have a causal relationship with this treatment.

An AE can therefore be any unfavorable and unintended sign (including an abnormal laboratory finding), symptom, or disease temporally associated with the use of an IMP, whether or not considered related to the IMP.

Medical disorders present at the time of signing the informed consent are only considered AEs if they worsen after this time. All baseline conditions should be recorded as part of Medical History.

All AEs occurring after the initiation of the treatment are referred to as treatment-emergent AEs (TEAEs). All AEs occurring prior to the initiation of the treatment will be referred to as non-TEAEs, which include any unintended sign, symptom, or disease that occurs between the screening and the first IMP administration of the clinical study. A TEAE also includes an AE present prior to administration of IMP which worsened after administration of IMP.

12.1.2 Adverse Reaction

All untoward and unintended responses to an IMP related to any dose administered.

All AEs judged by either the reporting Investigator or the Sponsor as having a reasonable causal relationship to a medicinal product qualify as adverse reactions. The expression reasonable causal relationship means to convey in general that there is evidence or argument to suggest a causal relationship.

12.1.3 Unexpected Adverse Reaction

An adverse reaction, the nature or severity of which is not consistent with the applicable product information (e.g., Investigator's Brochure for an unauthorized IMP or summary of product characteristics for an authorized product).

When the outcome of the adverse reaction is not consistent with the applicable product information this adverse reaction should be considered as unexpected.

12.1.4 Serious Adverse Event

Any untoward medicinal occurrence or effect that at any dose:

- Results in death
- Is life-threatening
- Requires hospitalization or prolongation of existing hospitalization
- Results in persistent or significant disability or incapacity
- Is a congenital anomaly or birth defect

Date: 13 December 2023

Sponsor: Atlas Molecular Pharma S.L. Study Code: ATL001-PI-CEP

NCT No.: 05647343

"Life-threatening" in the definition of a SAE or serious adverse reaction refers to an event in which the subject was at risk of death at the time of event; it does not refer to an event which hypothetically might have caused death if it was more severe.

Medical judgement should be exercised in deciding whether an AE/reaction is serious in other situations. Important AEs/reactions that are not immediately life-threatening or do not result in death or hospitalization but may jeopardize the subject or may require intervention to prevent one of the other outcomes listed in the definition above, should also be considered serious.

